16.35 Data & Safety Monitoring

16.351 The principal investigator(s) and the study statistician will review the study at least every quarter to identify accrual, adverse events, and any endpoint problems that might be developing. The Mayo Clinic Cancer Center (MCCC) Data Safety Monitoring Board (DSMB) is responsible for reviewing accrual and safety data for this trial at least twice a year, based on reports provided by the MCCC Statistical Office.

16.352 Adverse Event Stopping Rule: The stopping rule specified below is based on the knowledge available at study development. We note that the rule may be adjusted in the event of either (1) the study re-opening to accrual or (2) at any time during the conduct of the trial and in consideration of newly acquired information regarding the adverse event profile of the treatments under investigation. The study team may choose to suspend accrual because of unexpected adverse event profiles that have not crossed the specified rule below.

Accrual will be temporarily suspended to this study if at any time we observe events considered at least possibly related to study treatment (e.g., an adverse event with attribute specified as "possible," "probable," or "definite") that satisfy either of the following:

- If 3 or more of the first 12 treated patients experience a grade 4 or higher non-hematologic adverse event at least possibly related to treatment.
- If after the first 12 patients have been treated, 25% of all patients experience a grade 4 or higher non-hematologic adverse event at least possibly related to treatment.

We note that we will review grade 4 and 5 adverse events deemed "unrelated" or "unlikely to be related," to verify their attribution and to monitor the emergence of a previously unrecognized treatment-related adverse event.

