10.43 EXPECTED Serious Adverse Events: Protocol Specific Exceptions to Expedited Reporting

For this protocol only, the following Adverse Events/Grades are expected to occur within this population and do not require Expedited Reporting. These events must still be reported via Routine Reporting (see Section 10.6). *

| CTCAE SOC | Adverse Event | Grade | Attribution | Comments |
|--------------------------------------|----------------------------|--------------|------------------------------|---|
| Investigations | Neutrophil count decreased | Grade 3 or 4 | Possible, probable, definite | This frequent event in patients with CLL will be reported through the routine reporting mechanism |
| | Platelet count decreased | Grade 3 or 4 | Possible, probable, definite | This frequent event in patients with CLL will be reported through the routine reporting mechanism |
| | White blood count | Grade 3 or 4 | Possible, probable, definite | This frequent event in patients with CLL will be reported through the routine reporting mechanism |
| | Lymphocyte count decreased | Grade 3 or 4 | Possible, probable, definite | This frequent event in patients with CLL will be reported through the routine reporting mechanism |
| Blood and lymphatic system disorders | Anemia | Grade 3 or 4 | Possible, probable, definite | This frequent event in patients with CLL will be reported through the routine reporting mechanism |

*Report any clinically important increase in the **rate** of a serious suspected adverse reaction over that which is listed in the protocol or investigator brochure as an expedited event.

*Report an expected event that is greater in severity or specificity than expected as an expedited event.

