10.52 Death

Note: A death on study requires both routine and expedited reporting regardless of causality, unless as noted below. Attribution to treatment or other cause must be provided.

Any death occurring within 30 days of the last dose, regardless of attribution to an agent/intervention under an IND/IDE requires expedited reporting within 24-hours.

Any death occurring greater than 30 days with an attribution of possible, probable, or definite to an agent/intervention under an IND/IDE requires expedited reporting within 24-hours.

Reportable categories of Death

- Death attributable to a CTCAE term.
- Death Neonatal: A disorder characterized by cessation of life during the first 28 days of life.
- Death NOS: A cessation of life that cannot be attributed to a CTCAE term associated with Grade 5.
- Sudden death NOS: A sudden (defined as instant or within one hour of the onset of symptoms) or an unobserved cessation of life that cannot be attributed to a CTCAE term associated with Grade 5.
- Death due to progressive disease should be reported as **Grade 5** **"Neoplasms benign, malignant and unspecified (including cysts and**

polyps) – Other (Progressive Disease)" under the system organ class (SOC) of the same name. Evidence that the death was a manifestation of underlying disease (e.g., radiological changes suggesting tumor growth or progression: clinical deterioration associated with a disease process) should be submitted.

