10.6 Required Routine Reporting

10.61 Baseline and Adverse Events Evaluations

Pretreatment symptoms/conditions to be graded at baseline and adverse events to be graded at each evaluation per CTCAE v4.0 grading **unless** otherwise stated in the table below:

| System Organ Class (SOC) | Adverse event/Symptoms | Baseline | Each evaluation |
|--------------------------------------|---------------------------|----------|-----------------|
| Investigations | Platelet count decreased* | X | X |
| Blood and lymphatic system disorders | Anemia* | X | X |

*** Grading will be performed by the study statisticians at the time of analysis based on the CLL toxicity grading scale for blood counts in Appendix V. Anemia grade per CTCAE will also be recorded for reporting purposes.**

10.62 Submit via appropriate MCCC Case Report Forms (i.e., paper or electronic, as applicable) the following AEs experienced by a patient and not specified in Section 10.6:

10.621 Grade 2 AEs deemed *possibly, probably, or definitely* related to the study treatment or procedure.

10.622 Grade 3 and 4 AEs regardless of attribution to the study treatment or procedure.

10.623 Grade 5 AEs (Deaths)

10.6231 Any death within 30 days of the patient's last study treatment or procedure regardless of attribution to the study treatment or procedure.

10.6232 Any death more than 30 days after the patient's last study treatment or procedure that is felt to be at least possibly treatment related must also be submitted as a Grade 5 AE, with a CTCAE type and attribution assigned.

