Appendix V Grading Scale for Hematologic Toxicity in CLL Studies

Non Hematologic Toxicity will be scored using NCI CTCAE (version 4.0) for toxicity and adverse event reporting.

Hematologic toxicity will be assessed using IWCLL/Hallek December 2008⁶

Grading scale for hematologic toxicity in CLL studies

| Grade* | Decrease in platelets† or Hb‡ (nadir) from pretreatment value, % | Absolute neutrophil count/ μ L§ (nadir) |
|--------|--|---|
| 0 | No change to 10% | ≥ 2000 |
| 1 | 11%-24% | ≥ 1500 and < 2000 |
| 2 | 25%-49% | ≥ 1000 and < 1500 |
| 3 | 50%-74% | ≥ 500 and < 1000 |
| 4 | $\geq 75\%$ | < 500 |

* Grades: 1, mild; 2, moderate; 3, severe; 4, life-threatening; 5, fatal. Death occurring as a result of toxicity at any level of decrease from pretreatment will be recorded as grade 5.

†Platelet counts must be below normal levels for grades 1 to 4. If, the platelet count is $< 20 \times 10^9/L$ ($20\ 000/\mu L$) at any level of decrease, this will be considered grade 4 toxicity unless a severe or life-threatening decrease in the initial platelet count (eg, $20 \times 10^9/L$ [$20\ 000/\mu L$]) was present pretreatment. In this case, the patient will not be evaluable for toxicity referable to platelet counts.

‡Hb levels must be below normal levels for grades 1 to 4. Baseline and subsequent Hb determinations must be performed before any given transfusions. The use of erythropoietin is irrelevant for the grading of toxicity but should be documented.

§If the absolute neutrophil count (ANC) reaches $< 1 \times 10^9/L$ ($1000/\mu L$), it should be judged to be grade 3 toxicity. Other decreases in the white blood cell count or in circulating neutrophils are not to be considered because a decrease in the white blood cell count is a desired therapeutic endpoint. A gradual decrease in granulocytes is not a reliable index in CLL for stepwise grading of toxicity. If the ANC was $< 1 \times 10^9/L$ ($1000/\mu L$) before therapy, then the patient will not be evaluable for toxicity referable to the ANC. The use of growth factors such as G-CSF is not relevant to the grading of toxicity but should be documented.

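### The accrual-suspension rule does not count a related death whose only CTCAE term is hematologic; the gap is narrow and one clause in each bullet closes it

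*Combined protocol and SAP*

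**What the plan says.** Section 16.352 opens the rule with "Accrual will be temporarily suspended to this study if at any time we observe events considered at least possibly related to study treatment" and then gives two triggers. The first is met when 3 or more "of the first 12 treated patients experience a grade 4 or higher non-hematologic adverse event at least possibly related to treatment". The second applies after 12 patients have been treated and is met when "25% of all patients experience a grade 4 or higher non-hematologic adverse event at least possibly related to treatment". Neither bullet mentions grade 5 events separately.

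Other sections show that a death can carry a hematologic term. The reportable categories in 10.52 include "Death attributable to a CTCAE term". Section 10.6232 says that a related death more than 30 days after the last treatment "must also be submitted as a Grade 5 AE, with a CTCAE type and attribution assigned". The hematologic scale in Appendix V states: "Death occurring as a result of toxicity at any level of decrease from pretreatment will be recorded as grade 5".

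Section 10.43 sets a different limit for expedited reporting. It says that "the following Adverse Events/Grades are expected to occur within this population and do not require Expedited Reporting", and its table lists the cytopenias at grade 3 or 4 only.

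**The concern.** The usual reason for keeping hematologic events out of a toxicity boundary in CLL is that low counts are frequent. Section 1.2 gives pooled grade 3 or 4 rates of 10.7% for neutropenia, 6.2% for thrombocytopenia and 5.5% for anemia. Counting them would trip the rule on expected findings. That reason does not extend to deaths.

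As written, any number of related deaths coded only as cytopenias could occur without moving either count. What is at stake is limited to whether new patients keep being enrolled while the safety picture is reviewed, because the rule governs accrual only. It matters mainly when such a death occurs alongside other counted events.

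**Working it through.** **Step 1: does any clause bring the death into the count?**

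- Both bullets of 16.352 carry the non-hematologic limit.
- The closing note of 16.352 reviews grade 4 and 5 events, but only those judged unrelated or unlikely to be related. A related death is outside it.
- Section 16.352 does not define the non-hematologic class. The table in 8.2 puts febrile neutropenia under blood and lymphatic disorders, apart from its row for other non-hematologic events, so a fatal febrile neutropenia could be read either way.

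So a related death with only a hematologic term contributes 0 to both counts.

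**Step 2: where it changes a decision.** Take 2 patients with related grade 4 non-hematologic events and 1 related hematologic-only death among the first 12. The present wording counts 2 of 12 and accrual continues. With grade 5 included the count is 3 of 12 and accrual is suspended. One or two such deaths with no other event stay below 3 under either wording.

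**Step 3: inputs for the probabilities.** From the documents: boundaries of 3 of 12 and 25% (16.352), and maximum accrual of 35 (16.22). The plan states no operating characteristics for this rule, so there is no figure to reproduce. Rates of counted events (3%, 5%, 10%) and of hematologic-only related deaths (0.5%, 1%, 2%) are assumptions.

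**Step 4: given exactly one such death in the first 12.** Let X be the number of counted patients among the other 11, binomial with rate p. The present rule needs X ≥ 3; the amended rule needs X ≥ 2. The difference is P(X = 2).

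| p | Now, P(X ≥ 3) | Amended, P(X ≥ 2) |
|---|---|---|
| 3% | 0.4% | 4.1% |
| 5% | 1.5% | 10.2% |
| 10% | 9.0% | 30.3% |

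**Step 5: unconditional chance of suspension by patient 35.** This is an exact binomial recursion with a check after each patient. It suspends at a count of 3 for n ≤ 12 and at 25% of n rounded up for n = 13 to 35 (4 at 13–16, 5 at 17–20, 6 at 21–24, 7 at 25–28, 8 at 29–32, 9 at 33–35). Deaths and other counted events are taken to fall in different patients, so their rates add.

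| Background | Death rate | Combined rate | Now | Amended |
|---|---|---|---|---|
| 3% | 1% | 4% | 0.5% | 1.2% |
| 5% | 0.5% | 5.5% | 2.2% | 2.8% |
| 5% | 1% | 6% | 2.2% | 3.6% |
| 5% | 2% | 7% | 2.2% | 5.4% |
| 10% | 1% | 11% | 13.5% | 17.0% |
| 0% | 1% | 1% | 0% | 0.02% |

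The recursion treats each outcome as known before the next patient enrols. Treatment runs for up to 36 cycles, so some events would come after accrual has closed. Real suspension chances are lower under both wordings.

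**The case against.** The strongest reply is that the scenario is close to hypothetical and already covered. A dangerous cytopenia usually does its harm through infection or bleeding. A related grade 4 sepsis or hemorrhage before death would put that patient in the count already. The fatal events described in sections 1.2 and 15.17 (infections, progressive multifocal leukoencephalopathy, Stevens-Johnson syndrome, arrhythmias, strokes) are all non-hematologic.

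The safeguards are also real. Section 10.52 states: "Any death occurring within 30 days of the last dose, regardless of attribution to an agent/intervention under an IND/IDE requires expedited reporting within 24-hours". It asks the same for later related deaths. The investigators and statistician review the study at least quarterly and the DSMB at least twice a year (16.351). The team may suspend accrual without a boundary crossing and may adjust the rule at any time (16.352). Toxicity enters any decision to terminate (16.25), and patients on treatment are protected by the dose and discontinuation rules (8.2, 8.3). Discretion can act on the first such death; the amended boundary cannot.

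Most of this stands, and it is why the point is minor. It does not remove the point. Each safeguard relies on judgement and none makes the death count toward the fixed boundary. The comparison with 10.43 is supporting only: that section concerns reporting, so it shows how the protocol treats grade 5 elsewhere and does not prove that 16.352 is inconsistent.

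**Conclusion.** The concern holds as a narrow gap in the wording. A related grade 4 non-hematologic event counts toward suspension and a related hematologic-only death does not, although the reason for excluding cytopenias applies only to non-fatal ones. The unconditional effect is small, at most a few percentage points in the scenarios tried. It is larger when one such death joins other events in the first 12. All of these sizes depend on assumed rates, since the documents give neither a rate for such deaths nor one for counted events. The efficacy design, sample size and analyses are unaffected. This is an improvement the sponsor could make, of low severity.

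**What to change.** In both bullets of 16.352, after the non-hematologic event, insert *or any grade 5 adverse event*, keeping the requirement that the event be at least possibly related. Keep the 3-of-12 and 25% boundaries and the rest of the rule. This also settles, for deaths, how febrile neutropenia is handled.

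The cost is one clause in each of two bullets at the next amendment, with the same data, study team and DSMB. The downside is a slightly higher chance of a temporary accrual suspension: an extra 1.4 percentage points (3.6% − 2.2%) by patient 35 under the assumed 5% background and 1% death rate.

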16.4 Results Reporting on ClinicalTrials.gov

At study activation, this study will have been registered within the "ClinicalTrials.gov" website. The Primary and Secondary Endpoints along with other required information for this study will be reported on ClinicalTrials.gov. For purposes of timing of the Results Reporting, the initial estimated completion date for the Primary Endpoint of this study is 2.5 years after the study opens to accrual. The definition of "Primary Endpoint Completion Date" (PECD) for this study is at the time the last patient registered has been followed for at least 6 months.

16.5 Inclusion of Women and Minorities

16.51 This study will be available to all eligible patients, regardless of race, gender, or ethnic origin.

16.52 There is no information currently available regarding differential effects of this regimen in subsets defined by race or gender, and there is no reason to expect such differences to exist. Therefore, although the planned analysis will, as always, look for differences in treatment effect based on racial and gender groupings, the sample size is not increased in order to provide additional power for subset analyses.

16.53 The geographical region served by Mayo Clinic has a population that includes approximately 3% minorities. Based on prior Mayo Clinic studies involving similar disease sites, we expect about 3-5% of patients will be classified as minorities by race, and about 30% of patients will be women. Expected sizes of racial by gender subsets are shown in the following table:

| Accrual Targets | | | |
|---|-------------------|--------------|--------------|
| Ethnic Category | Sex/Gender | | |
| | Females | Males | Total |
| Hispanic or Latino | 0 | 1 | 1 |
| Not Hispanic or Latino | 11 | 23 | 34 |
| Ethnic Category: Total of all subjects | 11 | 24 | 35 |
| Racial Category | | | |
| American Indian or Alaskan Native | 0 | 0 | 0 |
| Asian | 0 | 0 | 0 |
| Black or African American | 1 | 1 | 2 |
| Native Hawaiian or other Pacific Islander | 0 | 0 | 0 |
| White | 10 | 23 | 33 |
| Racial Category: Total of all subjects | 11 | 24 | 35 |

Ethnic Categories: **Hispanic or Latino** - a person of Cuban, Mexican, Puerto Rican, South or Central American, or other Spanish culture or origin, regardless of race. The term "Spanish origin" can also be used in addition to "Hispanic or Latino."
Not Hispanic or Latino

Racial Categories: **American Indian or Alaskan Native** - a person having origins in any of the original peoples of North, Central, or South America, and who maintains tribal affiliations or community attachment.
Asian - a person having origins in any of the original peoples of the Far East, Southeast Asia, or the Indian subcontinent including, for example, Cambodia, China, India, Japan, Korea, Malaysia, Pakistan, the Philippine Islands, Thailand, and Vietnam. (Note: Individuals from the Philippine Islands have been recorded as Pacific Islanders in previous data collection strategies.)
Black or African American - a person having origins in any of the black racial groups of Africa. Terms such as "Haitian" or "Negro" can be used in addition to "Black or African American."
Native Hawaiian or other Pacific Islander - a person having origins in any of the original peoples of Hawaii, Guam, Samoa, or other Pacific Islands.
White - a person having origins in any of the original peoples of Europe, the Middle East, or North Africa.

17.0 Pathology Considerations/Tissue Biospecimens:

17.1 Summary Table of Research Tissue Specimens to be Collected for this Protocol

| Correlative Study (Section for more information) | Mandatory or Optional | Type of Tissue to Collect | Block, Slides, Core, etc. (# of each to submit) | Visit 1: Baseline only | Process at site? (Yes or No) | Temperature Conditions for Storage /Shipping |
|--|--------------------------|--|---|------------------------------|---------------------------------------|---|
| Control DNA | Mandatory | Patient must be willing to provide one of the following samples: | | | | |
| | | Saliva/buccal swab from oral cavity | NA | X | No | Ambient |
| | | Skin biopsy (only if buccal swab is not able to deliver adequate DNA) | 3mm punch biopsy | X | yes | Ambient |
| | | Myeloid cells from the bone marrow (only if buccal swab is not able to deliver adequate DNA and a bone marrow is done as part of routine standard clinical test) | aspirate | X | yes | Ambient |

17.2 Correlative Tissue Collection

17.21 Standard 3mm skin biopsy tissue. Kits will not be provided for this protocol.

17.22 Oral buccal swab for normal DNA sample

17.221 The oragene kit will be used for collection saliva/buccal swab.

If slides will be submitted, include thickness of tissue, and type of slide (charged or uncharged). Do not coverslip unstained slides.

17.222 Sample can be shipped overnight at ambient temperature

17.223 samples will be shipped to [name]'s laboratory in [name]

18.0 Records and Data Collection Procedures

18.1 Submission Timetable

Initial Material(s)

| | Active-Monitoring Phase (Compliance with Test Schedule Section 4.0) |
|--|---|
| CRF | |
| On-Study | |
| Adverse Event - Baseline | |
| Measurement - Baseline | |
| Research Blood Submission - Baseline (See section 14.0) | |
| Research Bone Marrow Aspirate Submission - Baseline (See section 14.0) | |
| Bone Marrow Biopsy | |
| FISH Results - Baseline | |
| Quantitative Flow Cytometry | |
| Pre-induction and pre-registration immunophenotyping/pre-registration MRD reports including CD38 and ZAP-70 ^{1,2} | |
| IgVH Mutation Analysis Report ¹ | |
| Other Laboratory Results | |
| CLL FISH Report ¹ | |
| Bone Marrow Biopsy Report ¹ | |
| CT Scan Report ¹ | |
| Research Tissue Submission - Baseline | |
| Psychology and QOL Assessments - Baseline | |
| End of Active Treatment/Cancel Notification | Submit \leq 2 weeks after registration if withdrawal/refusal occurs prior to beginning protocol therapy |

1. Submit copy of the report, Attention: QAS for MC1481, [contact].
2. For patients who previously had full flow immunophenotyping performed and at pre-study workup had limited repeat flow immunophenotyping, submit a copy of both reports.

Test Schedule Material(s)

| CRF | Active-Monitoring Phase (Compliance with Test Schedule Section 4.0) | | |
|---|--|------------------------|----------------|
| | At each evaluation during treatment | At end of treatment | Observation |
| Evaluation/Treatment | X ² | X | |
| Evaluation/Observation | | | X ¹ |
| Nadir/Adverse Event | X | X | X |
| Measurement | X | X | X |
| Quantitative Flow Cytometry | X ⁴ | X | X |
| Research Blood Submission | X ⁴ (see Section 14.0) | X | |
| Research Bone Marrow Aspirate Submission | X ⁴ (see Section 14.0) | X | |
| Bone Marrow Biopsy | X ⁴ | X ⁴ | X ⁴ |
| Other Laboratory Results | X | X | X |
| Immunophenotyping/MRD Report ³ | X ⁴ | X ⁴ | |
| Bone Marrow Biopsy Report ³ | X ⁴ | X ⁴ | |
| CT Scan Report ³ | X ⁴ | X ⁴ | |
| Psychology and QOL Assessments | X ⁴ | X ⁴ | |
| End of Active Treatment/Cancel Notification | | X | |
| ADR/AER | At each occurrence (see Section 10.0) | | |

1. Complete at each evaluation during Observation (see Section 4.0).
2. Complete at each evaluation during Active Treatment (see Section 4.0).
3. Submit copy of the report, Attention: QAS for MC1481, [contact].
4. Complete when required per the test schedule.

Follow-up Material(s)

| CRF | Event Monitoring Phase ¹ | | | | |
|------------------|---|--|--|-------|--------------------|
| | q. 3 months until PD or subsequent treatment for CLL ² | At PD or subsequent treatment for CLL ² | q. 6 mos. after PD or subsequent treatment for CLL | Death | New Primary |
| Event Monitoring | X | X | X | X | At each occurrence |

1. If a patient is still alive 5 years after registration, no further follow-up is required.
2. Submit copy of documentation of progression to the Operations Office, Attention: QAS for MC1481, [contact].

